9. DATA COLLECTION

The study will be conducted in the Neuroscience Research Laboratory in the SAHP-[name]. Informed consent will be obtained prior to

the beginning of the study by the graduate student investigator and other IRB approved researchers. Participants will be recruited if they are adults (males and females) aged 20-40 years old with no pain for the normal group and with neck or upper quadrant pain no greater than 4/10 in the VAS for longer than three months, not receiving clinical pain treatment, have not taken pain medication within six hours of first session, have acute pain or contraindications for TENS.

Study participants will be assessed on visits one, two and three (visit three will be at the end of the thirty-day period).

During participant's visit one, two and three the following clinical assessments will be provided:

- The VAS for pain, a subjective measure of pain intensity
- The STAI-form Y is a definitive clinical measure of state and trait anxiety in adults.
- The NDI questionnaire that measures neck disability.
- JPE test which will measure cervical spine proprioception through the Noraxon myoMotionTM system instrument.

10. LABELING & STORAGE OF DATA & SPECIMENS

Hard copies will be stored in a locked file cabinet in a locked room in the clinic and computer data will be stored on an encrypted computer in a locked room in the clinic.

11. DATA ANALYSIS

All data will be analyzed using SPSS version 28.0. For quantitative data, we will use the statistical test ANOVA and for descriptive statistics we will use means and standard deviations. Also, an expert statistician will be consulted to accurately analyze and interpret the results. The alpha level will be set at 0.05.

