5. INCLUSION / EXCLUSION CRITERIA

Inclusion criteria: Subjects will be adults between 20-40 years of age currently enrolled as students at Loma Linda University. There will be three groups. The

normal group will include twenty subjects with no neck and/or quadrant pain. The control group will include twenty subjects with neck and/or upper quadrant chronic subclinical pain and the intervention group will include twenty subjects with neck and/or upper quadrant chronic subclinical pain.

Exclusion criteria: Individuals currently receiving clinical pain treatment, pain medications within six hours of data collection, acute pain (control and intervention groups), individuals with electrotherapy contraindications, and unwilling to receive daily SMS text message home program reminder. Exclusion criteria will be determined by self-report using a questionnaire.

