7. INFORMED CONSENT PROCESS

The informed consent will be conducted by [name] in the SAHP Neuroscience Research Laboratory with a single potential subject at a time. Participants will have the opportunity to ask questions before deciding to participate. Those participants who meet inclusion criteria will be identified by a code on all documents other than their signature on the informed consent. Twenty participants with no pain will be in the normal group. Forty participants with chronic subclinical neck or upper quadrant pain will be randomized (random number table will be used) into two groups: twenty subjects in the control group, and twenty subjects in the intervention group. All participants' records will be stored in a locked cabinet, in a locked office and stored on a secure drive.

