- 1) To measure the immediate and short-term effects of TENS on subclinical neck or upper quadrant pain with the VAS, anxiety with the State-Trait Anxiety Inventory for Adults™, disability with neck disability index (NDI), disability and cervical spine proprioception Noraxon 3D Inertial Motion Capture System in subjects 20-40 years of age.
- 2) To measure pain, anxiety, disability, and cervical spine proprioception in subjects with and without neck or upper quadrant pain.
- 3) To compare compliance of TENS home usage in groups with and without short message system (SMS), text message, reminders.

c. Procedures involved (Research Interventions)

There will be three groups as follows: twenty subjects with no pain in the normal group; forty subjects with chronic subclinical neck or upper quadrant pain will be randomized into two groups: twenty subjects in the control group, and twenty subjects in the intervention group. The intervention group will be further randomized into two groups: ten subjects will receive instructions for home use of TENS with daily SMS text message reminders and ten subjects will receive instructions for home use of TENS without SMS text message reminders. We will aim for an equal distribution of males and females in each group.

First session (Day 1): Before starting the procedures, participants complaining of pain that are greater than 4/10 in the VAS will be excluded from the study as this will be greater of what we consider to be subclinical pain based on literature review and if the pain has been present less than three months. In addition, if participants with pain less than 4/10 pain receiving clinical pain treatment, have taken pain medication

within six hours of first session, have acute pain or contraindications for electrical stimulation would be excluded from the study. Following completion of the signing procedures, all participants will be given brief explanations before administration of the questionnaires.

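### Objective 2 sets pain-free beside pain participants without randomisation, and the only stated method is ANOVA without covariates, so an age or sex difference could be read as a mark of subclinical pain

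*Protocol*

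**What the plan says.** Objective 2 (Protocol Section 8b) is "To measure pain, anxiety, disability, and cervical spine proprioception in subjects with and without neck or upper quadrant pain".

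The groups behind it are formed in two ways. Protocol Section 7 states "Twenty participants with no pain will be in the normal group", so these people enter by pain status. The same section states "Forty participants with chronic subclinical neck or upper quadrant pain will be randomized", 20 to control and 20 to intervention. Randomisation therefore covers intervention versus control and nothing else.

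Two design features bear on comparability. Section 5 restricts all participants to ages 20 to 40, with no matching or balancing on age. Section 8c says "We will aim for an equal distribution of males and females in each group"; this covers the normal group too, but no mechanism is given.

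On analysis, Protocol Section 11 says "For quantitative data, we will use the statistical test ANOVA" and adds that "an expert statistician will be consulted to accurately analyze and interpret the results". It names no covariate, matching or stratification. The SAP describes only intervention versus control. Its ANCOVA deals with baseline differences between those two arms in trait anxiety and left lateral flexion. It does not analyse the normal group.

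**The concern.** In a randomised comparison, baseline differences arise by chance and the test allows for them. That does not carry over to normal versus pain. Pain status may itself be related to age or sex, so sampling error does not bound the imbalance between the groups.

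If anxiety, disability or joint position error also varies with age or sex, an unadjusted difference mixes that variation with whatever goes with pain. The protocol's rationale says that subclinical pain can lead to anxiety, disability and impaired neck proprioception, so a reader would be inclined to attribute an unadjusted difference to pain. At stake is the interpretation of Objective 2. The estimate of the TENS effect is not involved.

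This is separate from the SAP's silence on the normal group. Running the protocol's ANOVA would fill that gap and still leave the contrast unadjusted.

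**Working it through.** The plan gives no figure for this contrast to reproduce. The SAP's sample size of 40 concerns the two randomised arms.

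**Inputs from the documents.** 20 pain-free and 40 with pain (Protocol Sections 5 and 7); ages 20 to 40 (Section 5); alpha 0.05 (Section 11), taken as two-sided because sidedness is not stated.

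**Assumed inputs.** An age gap of 4 years between pain-free and pain groups, and an outcome slope of 0.02 to 0.05 SD per year of age. Neither is in the documents.

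**Step 1: bias from age.** Bias = gap × slope.
- Low: 4 × 0.02 = 0.08 SD.
- High: 4 × 0.05 = 0.20 SD.

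**Step 2: precision.** For 20 v 40, SE = sqrt(1/20 + 1/40) = sqrt(0.075) = 0.274 SD.

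**Step 3: false-positive rate, pooled contrast.** With no true difference, the F statistic on 1 and 58 degrees of freedom has noncentrality bias²/0.075; the 5% critical value is 4.007.
- 0.08 SD: 0.0064/0.075 = 0.085, rejection rate 6.0%.
- 0.20 SD: 0.04/0.075 = 0.533, rejection rate 11.1%.

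**Step 4: the same biases in a three-group ANOVA.** The protocol has three groups and does not say that the pain arms are pooled. With 20 per group and means 0, b, b, the noncentrality is 20 × (2/3) × b², again 0.085 and 0.533, now on 2 and 57 degrees of freedom (critical value 3.159). The rejection rates are 5.6% and 9.0%.

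**Step 5: other assumptions.** Writing bias as (age–outcome correlation) × (age gap in SD), for 20 v 40:

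| Correlation | Gap (SD) | Bias (SD) | False-positive rate |
|---|---|---|---|
| 0.1 | 0.25 | 0.025 | 5.1% |
| 0.2 | 0.5 | 0.10 | 6.5% |
| 0.3 | 0.5 | 0.15 | 8.4% |
| 0.3 | 1.0 | 0.30 | 19.0% |

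The first row is negligible. The last needs a full SD of age separation, which is a lot within a 20-year range. If ages were uniform over 20 to 40, their SD would be 20/sqrt(12) = 5.8 years, so a 4-year gap is 0.69 SD, and a slope of 0.05 SD per year implies a correlation of 0.05 × 5.8 = 0.29.

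**Step 6: cost of adjusting.** Residual degrees of freedom go from 58 to 56. The difference detectable with 80% power goes from 0.780 to 0.781 SD if the two covariates explain nothing, and falls to 0.741 or 0.698 SD if they explain 10% or 20% of outcome variance. These values ignore correlation between age and group. With a 4-year gap and the uniform-age SD, that correlation widens the standard error by about 5%: sqrt((0.075 + 0.69²/58)/0.075) = 1.05.

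**The case against.** The strongest reply is that the documents show no problem, only the possibility of one. They report no age or sex imbalance and no relation between age or sex and any outcome. This stands: a reader might infer that demographic differences will be reported as effects of pain, but the text supports only that they could be.

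Second, Objective 2 says that outcomes will be measured; it does not say that groups will be compared. This stands as wording. Still, a pain-free group that gets no TENS and is assessed on Days 1, 8 and 30 has little use except as a comparator.

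Third, sex has an intended design control in every group, and recruiting students aged 20 to 40 from one university limits the age gap. This stands in part. If the sex aim is met, confounding by sex largely disappears and age is the main point. The aim has no stated mechanism, and age is restricted but not balanced.

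A reader might be tempted by a larger figure. Adding a sex bias of 0.10 SD (a 20-point gap in the share of women times an assumed 0.5 SD sex difference) brings the total to 0.18 to 0.30 SD and the 20 v 40 false-positive rate to 9.9% to 19.0%. That assumes the sex aim fails and that both biases run the same way; opposite signs would partly or wholly cancel. Shrinking the groups for the 15% attrition would also be wrong for a Day 1 outcome, which is measured before follow-up losses.

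Finally, Section 11 promises a statistician. It attaches no method to that consultation, and the SAP has no analysis of the normal group.

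**Conclusion.** The point holds in a limited form. The pain-free versus pain contrast is not randomised, ANOVA without covariates is the only method stated for it, and neither document plans adjustment for age or sex. A difference in age, or in sex if balance is not achieved, could be taken for a mark of subclinical pain.

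The size cannot be known from the documents. Under the assumed 4-year gap and slopes, age alone moves the false-positive rate from 5% to about 6% to 11% for the pooled contrast, or 5.6% to 9.0% for three groups. If the groups are alike in age, or age is unrelated to the outcome, it stays near 5%. Severity is low: intervention versus control is untouched, and the contrast serves a descriptively worded objective.

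**What to change.** Add a sentence or two to Protocol Section 11 or the SAP. For Objective 2, replace the plain ANOVA by a linear model of each Day 1 value (STAI, NDI, JPE) on pain status (normal versus the two pain arms combined), age and sex. Use the Day 1 values taken before the in-lab TENS session. Show age and sex by group. Report the adjusted difference with a 95% confidence interval and call it an association, since unmeasured differences remain. VAS is left out because the normal group must score 0 to enter, so that difference is built in.

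The cost is two degrees of freedom and a slightly wider standard error if age is correlated with group. No new data should be needed: age is required for eligibility, sex for the balance aim, and the SAP tabulates gender for the two randomised arms. This is an inference, because the assessment list in Protocol Section 9 names neither, so confirm that both are recorded for the normal group.

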12. RISK AND INJURY

Participating in this study will involve the following risks: this study may involve breach of your confidentiality, risk of falls, risk of fatigue during study procedures and discomfort with the application of pain reducing electrical stimulation. This study may involve breach of your confidentiality: your information will be kept in a locked cabinet, in a locked office and store on a secure drive. Risk of falls: all reasonable attempts will be made to prevent you from falling including supervision, as someone will stand closely beside you to provide you with physical assistance as needed, the floor in the neuroscience research laboratory is not slippery. Risk of fatigue during

study procedures: you will be offered rest breaks regularly if the investigators notice signs of fatigue on you. You will be instructed on the use and application of pain reducing electrical stimulation device.

13. BENEFIT(S)

We expect that participants will experience improvements in cervical spine range of motion and proprioception, decreased anxiety and neck disability, and all components of improving wholeness and health as participants carry out functional activities. The expected benefits of this study include the improve of quality of life and functional mobility in people with neck chronic pain. In addition, the study may provide evidence of the efficacious use of electrical stimulation as a non-pharmacological option for the management of chronic pain. This study is expected to provide through electrical stimulation an accessible, affordable, self-administered and non-pharmacological option for the management of chronic pain without the need to go to a clinic for the application of electrical stimulation.

14. COMPENSATION

Participants will receive a \$50 gift card at the completion of the study.

15. CONFIDENTIALITY

Efforts will be made to keep participants' personal information confidential, but we cannot guarantee absolute confidentiality. We will use a pseudonym throughout the study for all recorded data so participant's actual name will not be used. Participants will not be identified by name in any publications describing the results of this study. Data in hard copy will be kept in a locked file cabinet, in a locked office and electronic data will be stored on a secure drive and password protected.

16. LITERATURE REVIEW

As defined by the IASP pain is “an unpleasant sensory and emotional experience associated with, or resembling that associated with, actual or potential tissue damage.” (IASP, 2021) and one of the most common reasons people seek medical care is chronic pain. Approximately 50 million adults in United Stated have chronic pain affecting daily lives¹ posing public health problems in costs of pharmacological management.^{2,3} The financial cost to care for people with chronic pain is more costly than diabetes, cardiovascular and cancer combined.^{4,5}

Chronic pain is persistent or recurrent pain that last longer than 3 months in one or more locations in the body even beyond the period of the expected healing phase.^{6,7} Chronic pain can be affected by biological, psychological and social factors that are accompanied by anxiety, depression, frustration, deconditioning, functional disability, financial problems and opioid use problems.^{8,9} As people experience pain, that experience and manifestation of pain is unique to each individual and includes physical and psychological factors⁷ making the managing pain and chronic pain can a difficult thing to achieve.¹

Facing an opioid epidemic, the CDC reports that studies of 2 weeks to 6 months in duration that utilized effective non-pharmacological treatments for chronic pain were effective.¹⁰ Among the recommendations from the CDC for non-opioid and non-pharmacological treatments for pain, physical therapy is included.^{10,11} As physical therapists we find imperative to reinforce the use of non-pharmacologic options for pain relief in people that are tackling the difficult task of managing their pain to continue with their normal lives.

As mentioned previously, one of the most common reasons people seek medical care is chronic pain;¹ however, subclinical pain (mild, low irritability) generally does not prompt people to seek medical treatment.^{12,13,14} Subclinical pain can be measured by the VAS score of $\leq 3.4/10$.¹⁵ In addition, non-pharmacological treatments in physical therapy for chronic subclinical pain have not been studied extensively. Pain can lead to anxiety^{8,9} (which is often treated with pharmacological interventions) and avoidance of movement. Pain and local inflammation in the cervical spine or upper quadrant, coupled with avoidance of movement, can lead to reduced cervical spine proprioception. Pain and anxiety are often treated with pharmacological interventions.

We are interested in learning more about people living with “subclinical” pain. According to Grant et al and Browne et al.^{16,17} people with neck pain but are not yet receiving any treatment as having minor musculoskeletal or “subclinical” pain. Subclinical pain may increase anxiety^{18,19} and affect movement and also can lead to anxiety, disability and impaired neck proprioception.^{12,14,20,21}

People may as what those non-pharmacologic options that physical therapy can offer for pain management, especially for untreated subclinical pain? In the field of physical therapy biophysical agents are agents that apply forms of energy to “modulate or decrease pain” along with the reduction of “risk factors and

complications; enhance health, wellness, or fitness; enhance or maintain physical performance; or prevent or remediate impairments in body functions and structures, activity limitations, or participation restrictions.”²² Within the group of biophysical agents is the application and use of electrical currents, more specifically TENS.²²

TENS is the delivery of electrical current through intact skin to stimulate peripheral nerves.²³ TENS delivers electrical currents through the skin with the objective to stimulate peripheral nerves to prevent the transmission of nociceptive information to the brain and by this process achieve pain relief.^{24,25,26,27} One of the most accepted theories for the modulation of pain with the use of TENS is the “gate control theory of pain” by Melzack and Wall published in 1965.^{28,29} which explains pain relief by electrical stimulation.²⁸ The authors proposed that by using electrical currents to stimulate low-threshold A-beta axons, it will reduce pain by pre-venting the transmission of nociceptive information in the spinal cord and brainstem.²³ This theory also proposed that the SG in the dorsal horn of the spine acts as a gate control system before afferents influence T cells.²⁸ T cells then activate the system responsible for response and perception.²⁸ Large-diameter afferent nerve fibers (facilitates SG) and small-diameter afferent nerve fibers (inhibits SG) influence T cells.³⁰ TENS gives the clinician the option to select the depolarization of afferents nerves through the adjustment of parameters of electrical current deliver with electrodes through the skin.³⁰ Depolarizing large-diameter (A-beta) sensory afferent nerves via sensory TENS can help gate or block noxious input.^{30,31,32} TENS has been used for treating subclinical pain based on studies that have found superiority of TENS over placebo for chronic musculoskeletal pain.³³ Most importantly for our study, TENS is non-prescriptive battery-powered device that uses self-adhering electrodes on the surface of the skin to deliver electrical current. TENS is often self-administered, affordable and safe when compared to medications.²³

Despite electrical stimulation for pain modulation has been used for many years, there is an “efficacy-impasse” for clinical utilization of TENS, despite fifty years of published research.³⁴ There is an urgent need for randomized controlled trials to investigate TENS effectiveness.³⁴ Based on this need the purpose of this study is to investigate the effects of electrotherapy for improving cervical spine proprioception, reduce pain, anxiety, and disability in adults with subclinical neck or upper quadrant pain.

REFERENCES

1. Centers for Disease Control and Prevention Website. <https://www.cdc.gov/learnmorefeelbetter/programs/chronic-pain.htm>. Accessed April 8, 2022.

Data was analyzed using SPSS version 28.0. Assuming a moderate effect size of 0.3, a power of 0.80, an alpha of 0.05 and 15% dropout rate, the estimated sample size was 40 participants. Data was summarized using frequency (%) for qualitative variables, mean \pm standard deviation (SD) for continuous variables, and median (minimum, maximum) when the distribution was not approximately normal. The normality of the outcome variables was examined using the Shapiro wilk test and boxplots. The frequency distribution of gender between the two study groups was compared using Fisher's exact test. Mean baseline characteristics and outcome variables by study group was examined using independent t-test. Median VAS, NDI, and JPE rotation right were compared between the intervention and control groups using Mann-Whitney U test. For each study group, changes in mean outcome variables (cervical spine AROM, anxiety, neck proprioception, VAS, NDI) over time (post versus pre) were examined using paired t-test or Wilcoxon signed rank test when the distribution is not approximately normal. Changes in outcome variables by group (intervention versus control) overtime (post 2 weeks versus pre) were assessed using 2x2 mixed factorial analysis of variance (ANOVA). If there was a significant interaction between group and time, the changes are significantly different between the two groups. There was a significant difference in mean STAI_T and lateral flexion left between the intervention and control groups at baseline, thus this was controlled for baseline differences using analysis of covariance (ANCOVA). In the intervention group, we examined changes in outcome variables over time (pre versus post 30 minutes versus post 2 weeks) using repeated measures ANOVA or Friedman's test if the data was not approximately normal. If the results were significant, Bonferroni's post hoc comparisons were conducted, or Wilcoxon signed rank test were used to determine what times were significantly different. The level of significance was set at $p \leq 0.05$.

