6. SUBJECT RECRUITMENT & SCREENING

This study will have a sample size of 60 adults (males and females) between 20 to 40 years of age. This sample size will provide us with enough power to detect the needed effect size. The estimated attrition rate is 15 percent. The participants will be recruited from the student population at Loma Linda University via flyers, posters, hand-outs, mass emails, and word of mouth. The phone script will be used when potential subjects contact us after seeing the flyer.

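### Does the SAP's sample size of 40 need correcting because its effect size of 0.3 has no stated metric, test, outcome or pre-post correlation?

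*SAP*

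**What the plan says.** The SAP is a single unheaded section. Its sample-size sentence takes a "moderate effect size of 0.3, a power of 0.80, an alpha of 0.05 and 15% dropout rate, the estimated sample size was 40 participants". The same section then lists several tests: independent and paired t-tests with rank alternatives, a 2x2 mixed ANOVA, ANCOVA, and a three-time-point repeated measures ANOVA within the intervention group. It applies the pre-post tests to "changes in mean outcome variables (cervical spine AROM, anxiety, neck proprioception, VAS, NDI) over time". None of these tests or outcomes is tied to the sample-size sentence. The group comparison of change rests on the 2x2 interaction: "If there was a significant interaction between group and time, the changes are significantly different between the two groups".

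Protocol section 6 gives a total of 60 adults and 15 percent attrition, and adds "This sample size will provide us with enough power to detect the needed effect size", without naming an effect, test or comparison. Protocol section 7 explains the two totals: "Forty participants with chronic subclinical neck or upper quadrant pain will be randomized" into two groups of twenty, and the other twenty are pain-free and not randomised.

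**The concern.** An effect size has no meaning without its metric. A value of 0.3 could be a standardised mean difference, an ANOVA f, a correlation or something else, and the sample sizes these imply differ several-fold. For a repeated-measures test the pre-post correlation also enters the calculation, and neither document gives one.

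The stake is interpretation. A reader who sees a moderate effect and 80% power may assume that the trial could detect a moderate difference between the groups. The reader may then take a non-significant interaction as evidence against one. If the real target was about one SD of the change score, that inference would be unsafe.

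**Working it through.** **Inputs from the documents.** Effect size 0.3, power 0.80, alpha 0.05, 15% dropout and N = 40 (SAP); two randomised groups of 20 (Protocol section 7); a 2x2 group-by-time interaction as the between-group test of change (SAP). **Assumed:** the metric, a two-sided (F) test and the correlation ρ.

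**1. Can 40 be reproduced?** Removing 15% from 40 leaves 40 × 0.85 = 34 evaluable, 17 per arm. Read 0.3 as f for the 2x2 interaction, with noncentrality λ = f² × N × 2/(1 − ρ) and degrees of freedom 1 and N − 2. At ρ = 0.3 and N = 34:

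- λ = 0.09 × 34 × 2/0.7 = 8.74, and power is 0.818.
- At the next smaller even total, N = 32, λ = 0.09 × 32 × 2/0.7 = 8.23 and power is 0.793, below 0.80.

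So 34 is the smallest even total that reaches 80%, and 34/0.85 = 40 exactly.

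**2. How much depends on ρ?** Same inputs, totals rounded up to even:

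| Assumed ρ | Evaluable N | Recruited N |
|---|---|---|
| 0 | 46 | 56 |
| 0.1 | 42 | 50 |
| 0.2 | 38 | 46 |
| 0.3 | 34 | 40 |
| 0.4 | 30 | 36 |
| 0.5 | 24 | 30 |
| 0.6 | 20 | 24 |
| 0.7 | 16 | 20 |

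On this reading 34 and 40 arise only for ρ of about 0.27 to 0.31.

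**3. Is that the only reading that keeps 0.3?** No. A two-group, three-time interaction has λ = f² × N × 3/(1 − ρ) and degrees of freedom 2 and 2(N − 2). At ρ = 0.1 and N = 34, λ = 0.09 × 34 × 3/0.9 = 10.2 and power is 0.804, which again gives 34 and 40. It does so for ρ of about 0.1 to 0.145. The protocol has three assessment visits, so this is a plausible calculation at the design stage, although the SAP's own three-time analysis is confined to the intervention group. Two other readings cannot have produced 40: a standardised mean difference of 0.3 needs 352 and a plain two-group f of 0.3 needs 90, both before dropout.

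**4. What can the trial detect?** The 2x2 interaction is the two-sample t-test on change scores, so the number per arm fixes the answer without any view on ρ. For n per arm and a difference of d SD of the change score, λ = n × d²/2. The 95% interval half-width is t(0.975, 2n − 2) × √(2/n).

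| Per arm | Difference at 80% power (SD of change) | Power for 0.5 SD | 95% CI half-width (SD of change) |
|---|---|---|---|
| 17 | 0.99 | 29% | 0.70 |
| 18 | 0.96 | 31% | 0.68 |
| 19 | 0.93 | 32% | 0.66 |
| 20 | 0.91 | 34% | 0.64 |

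The 0.5 SD column is illustrative; the documents name no such benchmark. As a cross-check with step 1, f = 0.3 at ρ = 0.3 corresponds to 0.3 × √(8/0.7) = 1.01 SD of the change score.

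**The case for a change.** The case for a change is that the omission is plain and matters. One missing number moves the recruited total from 56 to 20. Whichever reading produced 34 evaluable, the 2x2 test then has 80% power only for a difference of about one SD of the change score, and for 0.5 SD its power is 29% to 34%. The SAP decides by significance and plans no confidence interval for the difference in change. Protocol section 6 attaches its power claim to 60 people, 20 of whom are not randomised. A few words would let the reader see all this.

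The omission and the arithmetic stand. The case for a change is weaker than it looks, for four reasons.

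- The one-SD figure restates the sample size. Once 34 evaluable, 80% power and alpha 0.05 are fixed in a two-group test of change, a value near 1.0 must follow. It does not reveal what the investigators meant to target.
- The SAP's rule runs one way: a significant interaction means that the changes differ. It does not say that a non-significant one shows they are alike, so there is no wrong rule to correct.
- A blanket warning that a non-significant interaction leaves a moderate effect open would not always be true. At 17 per arm, an observed difference of −0.25 SD has an interval of −0.25 ± 0.70, or −0.95 to 0.45. That is non-significant, yet it excludes a benefit of +0.5 SD. The observed interval decides, and a detectable difference calculated after data collection adds nothing to it.
- Nothing in the documents shows that the protocol's 60 and the SAP's 40 come from one calculation. Tying section 6 to the SAP's figure would assert a link that the record does not support.

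**Conclusion.** The concern does not call for a change. The sample-size sentence is under-specified and 40 cannot be verified from the documents alone. Yet 40 matches the number randomised, and it is returned exactly by the stated inputs under a reading that fits the SAP's own between-group test (f = 0.3, assumed ρ about 0.27 to 0.31). A three-time reading at an assumed ρ of about 0.1 to 0.145 returns it as well. Which of these was used, if either, is unknown, and every correlation here is an assumption.

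The SAP describes an analysis already done: it reports which baseline variables differed. Naming the metric, test, outcome and correlation now would be good reporting if the record survives, but recruitment, allocation, tests and estimates would stay as they are. The trial's limited precision, a 95% half-width of 0.70 to 0.64 SD of the change score with 17 to 20 per arm, is a reason to read its results by their intervals. Those figures assume two equal arms and apply to outcomes analysed by the 2x2 ANOVA; they do not carry over to outcomes handled by rank tests or ANCOVA.
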